8.2.4. Clinical Safety Laboratory Assessments

See [Appendix 2](#) for the list of clinical safety laboratory tests to be performed and the [SOA](#) for the timing and frequency. All protocol-required laboratory assessments, as defined in [Appendix 2](#), must be conducted in accordance with the laboratory manual and the [SOA](#). Unscheduled clinical laboratory measurements may be obtained at any time during the study to assess any perceived safety issues.

The investigator must review the laboratory report, document this review, and record any clinically relevant changes occurring during the study in the AE section of the CRF. Clinically significant abnormal laboratory findings are those which are not associated with the underlying disease, unless judged by the investigator to be more severe than expected for the participant's condition.

All laboratory tests with values considered clinically significantly abnormal during participation in the study or within 28 days after the last dose of study intervention should be repeated until the values return to normal or baseline or are no longer considered clinically significant by the investigator or medical monitor.

If such values do not return to normal/baseline within a period of time judged reasonable by the investigator, the etiology should be identified, and the sponsor notified.

See [Appendix 6](#) for suggested actions and follow-up assessments in the event of potential drug-induced liver injury.

No need to repeat a clinical laboratory assessment on Cycle 1 Day 1 if the baseline assessment was performed within 7 days prior to that date.

8.2.5. Pregnancy Testing

Pregnancy tests may be urine or serum tests but must have a sensitivity of at least 25 mIU/mL. Pregnancy tests will be performed in WOCBP at the times listed in the [SOA](#). Following a negative pregnancy test result at screening, appropriate contraception must be commenced, and a second negative pregnancy test result will be required at the baseline visit

prior to the participant's receiving the study intervention. Pregnancy tests will also be done whenever 1 menstrual cycle is missed during the active treatment period (or when potential pregnancy is otherwise suspected) and at the end of the study. Pregnancy tests may also be repeated if requested by IRBs/ECs or if required by local regulations.

If a participant requiring pregnancy testing cannot visit a local laboratory, a home urine pregnancy testing kit with a sensitivity of at least 25 mIU/mL may be used by the participant to perform the test at home, if compliant with local regulatory requirements. The pregnancy test outcome should be documented in the participant's source documents/medical records and relevant data recorded on the CRF. Confirm that the participant is adhering to the contraception method(s) required in the protocol.

8.2.6. Injection Site Tolerability Assessments

Assessments of the injection sites in the abdominal fat fold to monitor local tolerability to PF-07260437 SC injections will be performed for at least 1 hour following study drug administration in Cycle 1 (Days 1 and 15), as per the [Schedule of Activities](#). An assessment should also be performed 24 hours (\pm 1 hour) after the C1D1 dose. Injection site tolerability assessments for at least 1 hour post the PF-07260437 injection should continue after each dosing day visit in Cycle 2 and beyond, only if injection site pain or ISR characteristics continue to persist. The assessments should continue at regularly scheduled visits until the symptoms resolve. The injection sites will be assessed for erythema, induration, ecchymosis, injection site pain, injection site pruritus, or other observed characteristics after PF-07260437 administration. The diameter of the affected area will be measured, and the condition of the injection site will be recorded on the CRF. Any observed abnormality at the injection site will be judged by the investigator to determine if the event should also be reported as an adverse event. ISRs should be immediately photographed in color, with scaled ruler placed by the reaction, and these photographs should be included in the participant's source documentation. When appropriate, at the discretion of the investigator, a participant with an ISR may be referred for a dermatological consultation and skin biopsy may be obtained for future examination of the ISR.

If severe ISR or unexpected low exposure is encountered with SC dosing, alternative IV infusion administration cohorts may be considered after discussion between investigators and sponsor and approval from sponsor.

8.3. Adverse Events, Serious Adverse Events, and Other Safety Reporting

The definitions of an AE and an SAE can be found in [Appendix 3](#).

AEs may arise from symptoms or other complaints reported to the investigator by the participant (or, when appropriate, by a caregiver, surrogate, or the participant's legally authorized representative), or they may arise from clinical findings of the Investigator or other healthcare providers (clinical signs, test results, etc.).

The investigator and any qualified designees are responsible for detecting, documenting, and recording events that meet the definition of an AE or SAE and remain responsible to pursue

and obtain adequate information both to determine the outcome and to assess whether the event meets the criteria for classification as an SAE or caused the participant to discontinue the study intervention (see [Section 7.1](#)).

During the active collection period as described in [Section 8.3.1](#), each participant/legally authorized representative will be questioned about the occurrence of AEs in a nonleading manner.

In addition, the investigator may be requested by Pfizer Safety to obtain specific follow-up information in an expedited fashion.

8.3.1. Time Period and Frequency for Collecting AE and SAE Information

The time period for actively eliciting and collecting AEs and SAEs (“active collection period”) for each participant begins from the time the participant provides informed consent, which is obtained before the participant’s participation in the study (ie, before undergoing any study-related procedure and/or receiving study intervention), through and including a minimum of 28 calendar days, except as indicated below, after the last administration of the study intervention.

Follow-up by the investigator continues throughout and after the active collection period and until the AE or SAE or its sequelae resolve or stabilize at a level acceptable to the investigator.

For participants who are screen failures, the active collection period ends when screen failure status is determined.

If the participant withdraws from the study and also withdraws consent for the collection of future information, the active collection period ends when consent is withdrawn.

If a participant permanently discontinues or temporarily discontinues study intervention because of an AE or SAE, the AE or SAE must be recorded on the CRF and the SAE reported using the CT SAE Report Form.

Investigators are not obligated to actively seek information on AEs or SAEs after the participant has concluded study participation. However, if the investigator learns of any SAE, including a death, at any time after a participant has completed the study, and he/she considers the event to be reasonably related to the study intervention, the investigator must promptly report the SAE to Pfizer using the CT SAE Report Form.

8.3.1.1. Reporting SAEs to Pfizer Safety

All SAEs occurring in a participant during the active collection period as described in [Section 8.3.1](#) are reported to Pfizer Safety on the CT SAE Report Form immediately upon awareness and under no circumstance should this exceed 24 hours, as indicated in [Appendix 3](#). The investigator will submit any updated SAE data to the sponsor within 24 hours of it being available.

If a participant begins a new anticancer therapy, SAEs occurring during the above-indicated active collection period must still be reported to Pfizer Safety irrespective of any intervening treatment. Note that a switch to a commercially available version of the study intervention is considered as a new anticancer therapy for purposes of SAE reporting.

8.3.1.2. Recording Nonserious AEs and SAEs on the CRF

All nonserious AEs and SAEs occurring in a participant during the active collection period which begins after obtaining informed consent as described in [Section 8.3.1](#), will be recorded on the AE section of the CRF.

The investigator is to record on the CRF all directly observed and all spontaneously reported AEs and SAEs reported by the participant.

Reporting of AEs and SAEs for participants who fail screening are subject to the CRF requirements as described in [Section 5.4](#).

If a participant begins a new anticancer therapy, the recording period for nonserious AEs ends at the time the new treatment is started; however, SAEs must continue to be recorded on the CRF during the above-indicated active collection period. Note that a switch to a commercially available version of the study intervention is considered as a new anticancer therapy for the purposes of SAE reporting.

8.3.2. Method of Detecting AEs and SAEs

The method of recording, evaluating, and assessing causality of AEs and SAEs and the procedures for completing and transmitting SAE reports are provided in [Appendix 3](#).

Care will be taken not to introduce bias when detecting AEs and/or SAEs. Open-ended and nonleading verbal questioning of the participant is the preferred method to inquire about AE occurrences.

8.3.3. Follow-Up of AEs and SAEs

After the initial AE or SAE report, the investigator is required to proactively follow each participant at subsequent visits/contacts. For each event, the investigator must pursue and obtain adequate information until resolution, stabilization, the event is otherwise explained, or the participant is lost to follow-up (as defined in [Section 7.3](#)).

In general, follow-up information will include a description of the event in sufficient detail to allow for a complete medical assessment of the case and independent determination of possible causality. Any information relevant to the event, such as concomitant medications and illnesses, must be provided. In the case of a participant death, a summary of available autopsy findings must be submitted as soon as possible to Pfizer Safety.

Further information on follow-up procedures is given in [Appendix 3](#).

8.3.4. Regulatory Reporting Requirements for SAEs

Prompt notification by the investigator to the sponsor of an SAE is essential so that legal obligations and ethical responsibilities toward the safety of participants and the safety of a study intervention under clinical investigation are met.

The sponsor has a legal responsibility to notify both the local regulatory authority and other regulatory agencies about the safety of a study intervention under clinical investigation. The sponsor will comply with country-specific regulatory requirements relating to safety reporting to the regulatory authority, IRBs/ECs, and investigators.

Investigator safety reports must be prepared for SUSARs according to local regulatory requirements and sponsor policy and forwarded to investigators as necessary.

An investigator who receives SUSARs or other specific safety information (eg, summary or listing of SAEs) from the sponsor will review and then file it along with the SRSD(s) for the study and will notify the IRB/EC, if appropriate according to local requirements.

8.3.5. Environmental Exposure, Exposure During Pregnancy or Breastfeeding, and Occupational Exposure

Environmental exposure occurs when a person not enrolled in the study as a participant receives unplanned direct contact with or exposure to the study intervention. Such exposure may or may not lead to the occurrence of an AE or SAE. Persons at risk for environmental exposure include healthcare providers, family members, and others who may be exposed. An environmental exposure may include exposure during pregnancy, exposure during breastfeeding, and occupational exposure.

Any such exposure to the study intervention under study are reportable to Pfizer Safety within 24 hours of investigator awareness.

8.3.5.1. Exposure During Pregnancy

An EDP occurs if:

- A female participant is found to be pregnant while receiving or after discontinuing study intervention.
- A male participant who is receiving or has discontinued study intervention exposes a female partner prior to or around the time of conception.
- A female is found to be pregnant while being exposed or having been exposed to study intervention due to environmental exposure. Below are examples of environmental EDP:
 - A female family member or healthcare provider reports that she is pregnant after having been exposed to the study intervention by inhalation or skin contact.

- A male family member or healthcare provider who has been exposed to the study intervention then exposes his female partner prior to or around the time of conception.

The investigator must report EDP to Pfizer Safety within 24 hours of the investigator's awareness, irrespective of whether an SAE has occurred. The initial information submitted should include the anticipated date of delivery (see below for information related to termination of pregnancy).

- If EDP occurs in a participant or a participant's partner, the investigator must report this information to Pfizer Safety on the CT SAE Report Form and an EDP Supplemental Form, regardless of whether an SAE has occurred. Details of the pregnancy will be collected after the start of study intervention and until 10 weeks after the last dose.
- If EDP occurs in the setting of environmental exposure, the investigator must report information to Pfizer Safety using the CT SAE Report Form and EDP Supplemental Form. Since the exposure information does not pertain to the participant enrolled in the study, the information is not recorded on a CRF; however, a copy of the completed CT SAE Report Form is maintained in the investigator site file.

Follow-up is conducted to obtain general information on the pregnancy and its outcome for all EDP reports with an unknown outcome. The investigator will follow the pregnancy until completion (or until pregnancy termination) and notify Pfizer Safety of the outcome as a follow-up to the initial EDP Supplemental Form. In the case of a live birth, the structural integrity of the neonate can be assessed at the time of birth. In the event of a termination, the reason(s) for termination should be specified and, if clinically possible, the structural integrity of the terminated fetus should be assessed by gross visual inspection (unless preprocedural test findings are conclusive for a congenital anomaly and the findings are reported).

Abnormal pregnancy outcomes are considered SAEs. If the outcome of the pregnancy meets the criteria for an SAE (ie, ectopic pregnancy, spontaneous abortion, intrauterine fetal demise, neonatal death, or congenital anomaly in a live-born baby), the investigator should follow the procedures for reporting SAEs. Additional information about pregnancy outcomes that are reported to Pfizer Safety as SAEs follows:

- Spontaneous abortion including miscarriage and missed abortion;
- Neonatal deaths that occur within 1 month of birth should be reported, without regard to causality, as SAEs. In addition, infant deaths after 1 month should be reported as SAEs when the investigator assesses the infant death as related or possibly related to exposure to the study intervention.

Additional information regarding the EDP may be requested by the sponsor. Further follow-up of birth outcomes will be handled on a case-by-case basis (eg, follow-up on preterm infants to identify developmental delays). In the case of paternal exposure, the investigator will provide the participant with the Pregnant Partner Release of Information Form to deliver to his partner. The investigator must document in the source documents that the participant was given the Pregnant Partner Release of Information Form to provide to his partner.

8.3.5.2. Exposure During Breastfeeding

An exposure during breastfeeding occurs if:

- A female participant is found to be breastfeeding while receiving or after discontinuing study intervention.
- A female is found to be breastfeeding while being exposed or having been exposed to study intervention (ie, environmental exposure). An example of environmental exposure during breastfeeding is a female family member or healthcare provider who reports that she is breastfeeding after having been exposed to the study intervention by any unplanned direct contact with the product.

The investigator must report exposure during breastfeeding to Pfizer Safety within 24 hours of the investigator's awareness, irrespective of whether an SAE has occurred. The information must be reported using the CT SAE Report Form. When exposure during breastfeeding occurs in the setting of environmental exposure, the exposure information does not pertain to the participant enrolled in the study, so the information is not recorded on a CRF. However, a copy of the completed CT SAE Report Form is maintained in the investigator site file.

An exposure during breastfeeding report is not created when a Pfizer drug specifically approved for use in breastfeeding women (eg, vitamins) is administered in accord with authorized use. However, if the infant experiences an SAE associated with such a drug, the SAE is reported together with the exposure during breastfeeding.

8.3.5.3. Occupational Exposure

The investigator must report any instance of occupational exposure to Pfizer Safety within 24 hours of the investigator's awareness using the CT SAE Report Form regardless of whether there is an associated SAE. Since the information about the occupational exposure does not pertain to a participant enrolled in the study, the information is not recorded on a CRF; however, a copy of the completed CT SAE Report Form must be maintained in the investigator site file.

8.3.6. Cardiovascular and Death Events

Not applicable

8.3.7. Disease-Related Events and/or Disease-Related Outcomes Not Qualifying as AEs or SAEs

The following DREs are common in participants with advanced or metastatic BrCa, OvCa or endometrial cancer and can be serious/life threatening:

- Disease or neoplasm progression
- Brain metastases
- Malignant pleural or peritoneal effusion

Because these events are typically associated with the disease under study, they will not be reported according to the standard process for expedited reporting of SAEs even though the event may meet the definition of an SAE. These events will be recorded on the AE page in the participant's CRF within the appropriate time frame. These DREs will be monitored by a safety review committee, safety review team on a routine basis.

Note: However, if either of the following conditions applies, then the event must be recorded and reported as an SAE (instead of a DRE):

- The event is, in the investigator's opinion, of greater intensity, frequency, or duration than expected for the individual participant.

OR

- The investigator considers that there is a reasonable possibility that the event was related to study intervention.

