9.1.1. Estimands

9.1.1.1. Primary Estimand/Co-Primary Estimands

Primary Estimand (DLT) for Part 1:

DLT rate estimated based on data from DLT-evaluable participants during the DLT-evaluation period (28 days for regimen without priming; priming doses plus 2 full doses for regimen with priming) in Part 1.

Variable: Occurrence of DLTs. DLTs are defined in [Section 4.3.6](#)

Analysis population:

For the dose escalation without priming, DLT-evaluable participants defined as participants:

- who receive at least 1 dose of study treatment and experience DLT during the DLT-evaluation period (28 days),

OR

- who complete the DLT-evaluation period without DLT. Participants without DLTs who withdraw from study treatment before receiving at least 2 full doses of study drug for reasons other than treatment-related toxicity are not evaluable for DLT.

For the dose escalation with priming, DLT-evaluable participants defined as participants:

- who receive at least 1 dose of study treatment and experience DLT during the DLT-evaluation period (priming doses plus 2 full doses, eg, 42 days),

OR

- who complete the DLT-evaluation period without DLT. Participants without DLTs who withdraw from study treatment before receiving at least the priming dose and 2 full doses of study drug for reasons other than treatment-related toxicity are not evaluable for DLT.

Population-level summary measure: DLT rate defined as the number of DLT-evaluable participants with DLTs in the DLT-evaluation period divided by the number of DLT-evaluable participants in the DLT-evaluation period.

Primary Estimand for Parts 1 and 2:

Incidence of AEs estimated in the analysis population during the AE-evaluation period, defined as the time from the first dose to earliest of 28 days post last dosing date and day of new anti-cancer therapy-1 day.

Variable: Occurrence of AEs. AEs are defined in [Section 8.3](#).

Analysis population: Safety analysis set defined as participants who receive at least 1 dose of study treatment without regard to tolerability or duration of treatment.

Population-level summary measure: Incidence of AEs defined as the number of participants with AEs in the AE-evaluation period divided by the number of participants in the analysis population. AEs will be summarized by type, frequency, severity (as graded by NCI CTCAE version 5), timing, seriousness, and relationship to treatment.

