9.3.5.2. AEs

AEs will be graded by the investigator according to the CTCAE version 5 and coded using MedDRA. AE data will be reported in tables and listings. Summaries of AE by appropriate MedDRA terms, toxicity grade, and seriousness and relationship to study treatment will be presented, as well as summaries of AEs leading to death and premature withdrawal from study treatment. The number and percentage of participants who experienced any AE, SAE, treatment-related AE, and treatment-related SAE will be summarized according to worst toxicity grades. The summaries will present AEs both on the entire study period and by cycle (Cycle 1 and Cycles beyond 1). Listings of DLTs and deaths will be provided.

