
Any clinically significant abnormal laboratory findings or other abnormal safety assessments that are associated with the underlying disease, unless judged by the investigator to be more severe than expected for the participant's condition.The disease/disorder being studied or expected progression, signs, or symptoms of the disease/disorder being studied, unless more severe than expected for the participant's condition.Medical or surgical procedure (eg, endoscopy, appendectomy): the condition that leads to the procedure is the AE.Situations in which an untoward medical occurrence did not occur (social and/or convenience admission to a hospital).Anticipated day-to-day fluctuations of preexisting disease(s) or condition(s) present or detected at the start of the study that do not worsen.Worsening of signs and symptoms of the malignancy under study should be recorded as AEs in the appropriate section of the CRF. Disease progression assessed by measurement of malignant lesions on radiographs or other methods should not be reported as AEs.

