- Medical or scientific judgment should be exercised by the investigator in deciding whether SAE reporting is appropriate in other situations, such as significant medical events that but may jeopardize the participant or may require medical or surgical intervention to prevent one of the other outcomes listed in the above definition. These events should usually be considered serious.
- Examples of such events include invasive or malignant cancers, intensive treatment in an emergency room or at home for allergic bronchospasm, blood dyscrasias or convulsions that do not result in hospitalization, or development of drug dependency or drug abuse.
- Progression of the malignancy under study (including signs and symptoms of progression) should not be reported as an SAE unless the outcome is fatal within the active collection period. Hospitalization due to signs and symptoms of disease progression should not be reported as an SAE. If the malignancy has a fatal outcome during the study or within the active collection period, then the event

leading to death must be recorded as an AE on the CRF, and as an SAE with CTCAE Grade 5 (see the [Assessment of Severity](#) section).

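### Protocol 8.3.7 puts disease progression on the AE page, 10.3.1 bars measured progression from AE reporting, and neither document says whether such records count in the primary AE tables

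*Protocol*

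**What the plan says.** Protocol 8.3.7 is headed "Disease-Related Events and/or Disease-Related Outcomes Not Qualifying as AEs or SAEs". Its first listed event is "Disease or neoplasm progression"; brain metastases and malignant effusions follow. It takes these events out of the standard expedited SAE process and then says: "These events will be recorded on the AE page in the participant's CRF within the appropriate time frame". An event becomes an SAE instead if the investigator judges it worse than expected for that participant, or possibly related to study treatment. Death is not mentioned.

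Protocol 10.3.1, under events that do not meet the AE definition, says: "Disease progression assessed by measurement of malignant lesions on radiographs or other methods should not be reported as AEs". The same bullet also says: "Worsening of signs and symptoms of the malignancy under study should be recorded as AEs in the appropriate section of the CRF".

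Protocol 10.3.2 says progression is not an SAE unless it is fatal within the active collection period. If it is fatal, the event "leading to death must be recorded as an AE on the CRF, and as an SAE with CTCAE Grade 5".

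The primary AE estimand for both parts (Protocol 9.1.1.1, repeated in SAP 2.1.1) is: "Incidence of AEs defined as the number of participants with AEs in the AE-evaluation period divided by the number of participants in the analysis population". The results are then broken down by type, frequency, severity, timing, seriousness and relationship. SAP 6.1.2 treats every AE in the on-treatment period as treatment-emergent. SAP 6.6.1 takes death and SAE information from the CRF. Neither document has a flag, term list or exclusion for disease-related events.

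**The concern.** Progression will be common in this population, and the protocol gives sites two instructions for it. A site following 8.3.7 enters measured progression on the AE page. A site following 10.3.1 does not. Both comply with the protocol.

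AEs are a primary endpoint in both parts. In Part 2 the only primary endpoints are AEs and laboratory abnormalities, in cohorts of about 20. If the AE page feeds the TEAE tables without a filter, part of the difference between cohorts or dose levels could reflect site recording habits. For fatal progression, SAE status and the 24-hour reporting duty in Protocol 8.3.1.1 also depend on which section is followed. Mixed practice would be hard to separate after the data have accrued.

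**Working it through.** The plan states no figure on this point, so there is nothing to reproduce. The check sets the rules side by side and then sizes the effect under stated assumptions.

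**1. The rules side by side**

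| Situation | Protocol 8.3.7 | Protocol 10.3.1 and 10.3.2 |
|---|---|---|
| Measured progression, non-fatal, as expected, unrelated | AE page; no expedited SAE report | Not reported as an AE; not an SAE |
| Progression, non-fatal, worse than expected or possibly related | Recorded and reported as an SAE | Not an SAE, because not fatal |
| Progression fatal in the active collection period, as expected, unrelated | AE page; no expedited SAE report; grade not stated | AE on the CRF and a Grade 5 SAE |
| Worsening signs and symptoms of the malignancy | Not listed as such | Recorded as AEs |

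The first row is a conflict over AE recording. The second and third are conflicts over SAE status, in opposite directions. The fourth is not a conflict between the sections. However, another 10.3.1 bullet says that expected signs and symptoms of the disease are not AEs, so the boundary is unclear there too.

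**2. Route to the analysis**

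The estimand counts participants with AEs. The SAP counts any on-treatment AE and takes SAE and death data from the CRF. No step between the AE page and the TEAE table removes a disease-related event. Whether such a record enters the table is therefore undefined.

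**3. Size in the progression row (assumed rates)**

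Inputs: n = 20 per Part 2 cohort (Protocol 9.5.2). The share progressing inside the AE window, q, is not given in the documents and is taken as 0.2 to 0.8. Intervals are Clopper-Pearson, the exact method named in SAP 5.2.1.

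| Section followed | Assumed q | Row | 95% CI |
|---|---|---|---|
| 10.3.1 | any | 0/20 = 0% | 0 to 16.8% |
| 8.3.7 | 0.2 | 4/20 = 20% | 5.7 to 43.7% |
| 8.3.7 | 0.5 | 10/20 = 50% | 27.2 to 72.8% |
| 8.3.7 | 0.8 | 16/20 = 80% | 56.3 to 94.3% |

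This treats all progression in the window as measured progression and all sites in the cohort as following the same section. Mixed practice would fall in between.

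**4. Size in the any-AE proportion**

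Let a be the share of participants with some other AE, taken as independent of progression. Recording progression adds only participants who had no other AE:

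shift = (1 − a) × q

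| a | q = 0.2 | q = 0.5 | q = 0.8 |
|---|---|---|---|
| 80% | 4 points | 10 points | 16 points |
| 90% | 2 points | 5 points | 8 points |
| 95% | 1 point | 2.5 points | 4 points |
| 100% | 0 | 0 | 0 |

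The effect is mainly on the breakdown by type, severity and seriousness, not on the headline proportion.

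**The case against.** The best defence is that recording an event on the AE page is not the same as reporting it as an AE. The 8.3.7 heading supports this. Protocol 8.3.10 offers a parallel: medication errors go on a version of the AE page whether or not an AE occurred. CRF detail also sits in a completion document (Protocol 10.1.7) that is not available here. So it is an inference that everything on the AE page reaches the primary tables. That is fair, but the reading protects the endpoint only if these records are flagged and excluded, and neither document says so. It also leaves the SAE conflicts untouched.

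It can also be said that the AE conflict is narrow, since 10.3.1 bars only measured progression, and that 10.3.2 gives the more specific rule for a fatal outcome. Both points stand. On a fatal outcome the sections agree that the event goes on the CRF; they differ on its SAE status and reporting.

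Three stronger readings are tempting and are not supported:

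- **AE incidence could differ by about 90 points between sites.** A reader might take the 5.4-month median PFS in Protocol 4.2.2 and compute 1 − 2^(−24/5.4) = 0.954 over two years of treatment. That median is for first-line TNBC, PFS counts deaths as well as progressions, and participants who stop for other reasons may progress after the AE window closes. Even if it were right, it would describe one row of a table, not the estimand.
- **The table of AEs leading to withdrawal would fill with progressions.** Protocol 9.3.5.2 does plan "summaries of AEs leading to death and premature withdrawal from study treatment". But Protocol 7.1 lists progression and unacceptable toxicity as separate reasons for stopping treatment, and SAP 6.5.2 tabulates discontinuation by reason. Nothing shows that a progression record would be coded as an AE leading to withdrawal.
- **Dose decisions would shift.** DLTs must be treatment-related and not reasonably attributable to the underlying disease (Protocol 4.3.6), and deaths clearly due to disease are excluded (4.3.6.2). The accrual-halt example in 4.4 requires possible relatedness. Any influence would come only through general review of safety data.

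**Conclusion.** The inconsistency is real and lies in current protocol text. Sections 8.3.7 and 10.3.1 disagree on whether measured progression belongs with AEs. Sections 8.3.7 and 10.3.2 disagree on when progression is an SAE, including when it is fatal. The estimand and the SAP do not resolve either question, so two compliant sites can produce different AE, SAE and Grade 5 entries.

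The consequence is limited. The single progression row could range from none to most of a cohort, on assumed progression rates of 20% to 80% that the documents neither give nor exclude. The any-AE proportion would change by a few points at most if, as assumed, 90% or more of participants have another AE: up to 8 points at 90% and up to 4 at 95%. The study tests no hypothesis, and the DLT and accrual-halt rules are essentially untouched. The point needs correcting because it concerns the content of primary safety tables and a safety-reporting duty, and because the correction is cheap.

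**What to change.** Reconcile Protocol 8.3.7, 10.3.1 and 10.3.2 into one rule that says where progression, brain metastases and malignant effusions are recorded, when they become AEs or SAEs, and how fatal progression is recorded and reported. The choice of SAE rule is the sponsor's; the three sections need to state the same one.

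In SAP 6.1.2 and 6.6.1, state that disease-related events meeting no 8.3.7 exception are excluded from the TEAE tables and listed separately. Say explicitly whether fatal progression appears in the Grade 5, SAE and AE-leading-to-death tables. If these records stay on the AE page, the CRF needs a way to identify them.

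The cost is protocol and SAP wording, a line in the CRF completion instructions and one extra listing. It is best done before data accrue.
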